The primary objective is to assess the effect of the ROSF formulation, if any, on swallowing safety in subjects with ALS. The null hypothesis is that there will be no difference between the PAS scores (i.e. swallowing safety) obtained before and after administration of the study medication.

The PAS scores obtained in swallow tests during VFSS 1-PAS (before ROSF) and VFSS 2-PAS (after ROSF) will be compared within each subject with the non-parametric Wilcoxon Signed-Rank Test. Alpha will be set at 0.05, two-tailed. Analysis across each swallowing trial will be performed, providing 12 bolus stimuli trials and approximately 35 swallows and PAS scores for each elicited swallow across testing within each participant (across various textures and swallowing complexities given that multiple swallows are typically elicited per bolus stimuli trial) to ensure a comprehensive exam across a variety of liquid volumes, textures and consistencies).

CONFIDENTIAL INFORMATION

The information in this study protocol is confidential. Any disclosure, copying or distribution of the information contained within is strictly prohibited without written consent from MonoSol Rx LLC.

Sample size was determined for a within-person design (repeated measures, same subjects in VFSS 1-PAS and VFSS 2-PAS) using G*Power Version 3.1.9.2, assuming a correlation = 0.6 across the two measurements. A sample size of n=25 would be able to detect at least a 1.0 point difference (two-tailed), effect size 0.6, in PAS scores from Test 1 and Test 2 with 80% power. It is anticipated that approximately 20% of recruited ALS subjects will grossly aspirate during VFSS 1-PAS and will not have a VFSS 2-PAS performed (for both safety reasons and also because Test 2 would not yield any useful data due to a ceiling effect). Therefore enrollment is planned for a total of 30 subjects to account for this potential.

Depending on the study enrollment rate, the Sponsor may elect to perform an interim analysis using available data from the subset of subjects who have completed the study at that time. The results of this interim analysis will be used only for internal planning and possibly for sharing with regulatory authorities. The results of the interim analysis will have absolutely no influence on the subsequent conduct of the study.

The following safety information will be included as descriptive summaries:

- Type, incidence, and severity of adverse events
- Physical and neurological examinations

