1. INTRODUCTION

This statistical analysis plan (SAP) is intended to give a detailed description of the summaries and the analyses that will be generated for the present study by inVentiv Health Clinical. Analyses specified in this plan are based on Protocol 17MO1R-0012 Version 2.0, Amendment I, dated 18 October 2017. Safety and tolerability analyses will be described.

The original plan has changed as described below. Further details are documented in the remainder of this document. These changes will also be described in the clinical study report (CSR).

Top-line clinical results from the Videofluoroscopic Swallowing Study (VFSS) for the first 7 completed patients were presented to the Food and Drug Administration (FDA) on Sept 10 2018. At that time, two additional patients had been enrolled but had not yet undergone the VFSS. On Sept 12 2018, the FDA agreed with the Sponsor that due to the lack of any signal of detrimental effect on VFSS after one dose of study drug, the study would be terminated after the completion of 9 patients (the seven completed by Sept 10 and the two additional patients in screening at that time). In addition to the lack of signal of any harmful effect, the Agency and the Sponsor took into account the difficulty and hardship involved for these disabled patients in participating in the study, the potential risks of participation (including possible reaction to barium, potential for aspiration, and exposure to radiation), and the fact that the participating patients would derive no direct benefit for participation.

When applicable, all methodology and related processes will be conducted according to Standard Operating Procedures (SOPs) of InVentiv Health Clinical.

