5.1 Safety Population

The safety population is defined as the group of subjects who receive the study medication.

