6.2 Determination of Sample Size

The original protocol specified that approximately thirty (30) subjects with ALS would be recruited to obtain a final sample size of at least 25 completed. As previously noted, the Sponsor and FDA have agreed to terminate the study with a completed sample size of 9 subjects.

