6.5 Safety Analysis

Safety data will be evaluated through the assessment of PAS scores on the VFSS, adverse events (AEs), clinical signs and symptoms from physical and neurological examination following study drug administration, and vital signs assessments. Treatment-Emergent Adverse Events (TEAEs), and vital signs, will be summarized. No inferential analysis will be carried out for the safety data.

Shells for all tables and listing referred to in this section are displayed in separate document.

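### The SAP discloses the stop at 9 completers but not that it departs from the protocol's no-influence clause, and it plans no measure of precision for the primary PAS outcome

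*Protocol*

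**What the plan says.** **Interim.** The protocol (Synopsis, Statistical Analysis, and again in 13.5.2) lets the sponsor look at available data, depending on the enrolment rate. It limits the use of that look to internal planning and possible sharing with regulators, and adds: "The results of the interim analysis will have absolutely no influence on the subsequent conduct of the study". The target is 25 completers from about 30 enrolled (protocol 13.3).

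**Stop.** SAP section 1 says that VFSS results for the first 7 completers went to the FDA on 10 September 2018. On 12 September the FDA agreed that, "due to the lack of any signal of detrimental effect on VFSS after one dose of study drug, the study would be terminated" once 9 patients had completed. Other reasons follow: "In addition to the lack of signal of any harmful effect, the Agency and the Sponsor took into account the difficulty and hardship involved", along with the risks of taking part and the lack of direct benefit. Section 1 calls this a change to the plan and commits to describing it in the clinical study report. SAP 6.2 repeats that "the Sponsor and FDA have agreed to terminate the study with a completed sample size of 9 subjects", and 6.5.8 describes the look after 7 as unofficial. SAP 6.6, the section for changes from the protocol, refers back to the previous sections on this and does not mention the clause.

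**PAS analysis.** The protocol planned a two-sided Wilcoxon signed-rank test. SAP 6.5.8 makes the analysis descriptive. It lists three methods (single worst score, sum of 11 scores, four-category grouping of the worst score), each reported as the number and percentage of patients unchanged, increased or decreased, and by how much. The SAP states that these methods were settled post hoc, when the first seven patients' results were examined. SAP 6.5 counts PAS as safety data ("Safety data will be evaluated through the assessment of PAS scores on the VFSS") and then says: "No inferential analysis will be carried out for the safety data".

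**Denominator.** SAP 5 bases safety analyses on the safety population, and 5.1 says "The safety population is defined as the group of subjects who receive the study medication". SAP 6.1.2 rules out imputation. Section 6.5.8 names no denominator for PAS change.

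**The concern.** The trial asks one question: does the film make swallowing less safe? Two things limit how its answer can be read.

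First, a reader comparing the protocol with the SAP finds an unconditional statement that interim results will not affect conduct, and then a study ended mainly because of interim results. The SAP gives all the facts but never joins them to the clause, so the reader has to find the conflict unaided.

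Second, counts alone from nine subjects do not show what the study leaves open. Seven of the nine are the subjects whose results led both to the stop and to the choice of summary methods. A bare statement that few or none worsened could be taken as evidence of safety when a substantial risk remains compatible with the data.

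**Working it through.** **1. The plan's own figure.** Inputs (protocol Synopsis and 13.5.3): effect size 0.6, a 1.0-point PAS difference, two-sided alpha 0.05, n = 25, power 80%. The implied SD of the differences is 1.0/0.6 = 1.67. Noncentral-t power for the signed-rank test, with n multiplied by 3/π (its relative efficiency for normal data):

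- n = 25: effective n = 25 × 0.955 = 23.9; noncentrality = 0.6 × √23.9 = 2.93; power 80.1%. The stated figure reproduces. Simulation of the exact test gives 79.9%.
- n = 9: effective n = 8.6; noncentrality = 1.76; power 33.7%. Simulation of the exact test gives 30.2%, and a paired t-test 35.4%.

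This is context only, because the SAP no longer plans a test.

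**2. What a count leaves open.** The documents report no PAS counts, so every count here is assumed. Two-sided 95% Clopper-Pearson limits; for zero events the upper limit is 1 − 0.025^(1/n):

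- 0 of 9: 1 − 0.025^(1/9) = 33.6%
- 0 of 25: 1 − 0.025^(1/25) = 13.7%
- 0 of 7: 41.0%
- 0 of 8 (if one of the nine lacked VFSS 2): 36.9%
- 1 of 9: 0.3% to 48.2%
- 2 of 9: 2.8% to 60.0%
- 1 of 25: 0.1% to 20.4%

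**3. Chance of seeing no worsening at all**, (1 − p)^n, for assumed true risks p:

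| p | n = 7 | n = 9 | n = 25 |
|---|---|---|---|
| 10% | 47.8% | 38.7% | 7.2% |
| 20% | 21.0% | 13.4% | 0.4% |
| 30% | 8.2% | 4.0% | under 0.1% |

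**4. The passages side by side.** Protocol 13.5.2 permits sharing the interim with regulators, so the discussion with the FDA was within the plan. What the clause excludes is the next step, in which the results shape conduct. In SAP section 1 the absence of a signal is the stated cause, and hardship, risk and lack of benefit are given as additional considerations. The stop was therefore led by the interim, though not based on it alone. No section of the SAP cites the clause.

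**5. Denominator.** A pre/post change needs both VFSS. Protocol 10.2.3 foresees subjects who leave after dosing and before VFSS 2. Everyone dosed and everyone with both examinations can therefore be different groups.

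**The case against.** **The change is on record.** A reader might infer that the SAP hides the departure. It does not: it reports the look, the number, the reasons, the FDA agreement and the intention to describe the change in the study report. What is missing is one sentence tying the stop to the clause.

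**The stop had other grounds.** A reader might also infer that the stop was not allowed. Protocol section 14 reserves the right to discontinue at any time for safety or administrative reasons, and the SAP's reasons include risks to participants. That does not remove the conflict with the no-influence clause, but a note naming the clause without section 14 would be one-sided.

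**No interval was ever promised.** The protocol planned only a test, even at 25. The table shells are in a separate document not available here, and anyone given the count and the denominator can compute the limits. This stands: the interval is an improvement, not a broken commitment. Dropping the test at n = 9 is reasonable, and a descriptive interval is consistent with not testing hypotheses.

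**The proportion worsening is a rough measure.** The protocol's own scale is the within-subject difference. With an SD of 1.67, a 95% interval for the mean change has a half-width of 2.306 × 1.67/√9 = 1.28 points at n = 9, against 2.064 × 1.67/√25 = 0.69 at n = 25. Any increase counts as worsening, including 1 to 2, both of which protocol Table 4 classes as safe. With an inert film and symmetric retest noise, the chance of an increase is (1 − tie rate)/2. At an assumed 40% of ties that is 30%, or 2.7 of 9 expected, and 3 of 9 would give 7.5% to 70.1%. For assumed tie rates of 20% to 60%, 0 of 9 would occur in only 1% to 13% of samples, so it is a favourable illustration. This also stands. It is why the interval should not be used as a formal ceiling on any conclusion: that would turn a descriptive, nominal quantity into an inferential one.

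**Conclusion.** The point holds in limited form, as a cheap improvement. The SAP discloses the stop but does not acknowledge that a stop led by the 7-subject look departs from protocol 13.5.2. It also plans no measure of precision for the primary PAS outcome.

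The size is illustrative, because it rests on assumed counts. With no worsening among nine, a risk up to 33.6% would remain inside the exact interval, about two and a half times the 13.7% for 25. Any other count also leaves a wide interval. The figures assume that all nine have both examinations, and they treat the sample size as fixed although stopping depended on results.

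The documents do not support inferring that the stop was concealed or improper, that the film is harmful, or that 33.6% is a result of this trial.

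**What to change.** - **SAP 6.5.8.** Add a two-sided 95% Clopper-Pearson interval for the proportion worsening under each of the three listed methods, for all 9 and for the first 7. Take subjects with both VFSS as the denominator. Label the intervals descriptive and nominal, because the stop and the choice of methods followed the 7-subject results. Note that any increase counts as worsening, so the proportion includes uncontrolled test-retest variation.
- **SAP 6.5.** Replace the bar on inference with a statement that no hypothesis tests will be done on safety data and that the intervals in 6.5.8 are descriptive.
- **SAP 6.6.** State that ending at 9 after the 7-subject look departs from the no-influence clause in protocol 13.5.2. In the same place cite protocol section 14, the further reasons and the FDA agreement. Report any statement of no harmful effect alongside the intervals.

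The cost is edits to three sections and six intervals (three methods, two sets of subjects). No new patients, data or endpoint are needed. The downside is that wide intervals make the result look less favourable, and they remain nominal.

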4. LIST OF ABBREVIATIONS

Abbreviation	Definition
AE	adverse event
ALS	amyotrophic lateral sclerosis
ALSFRS-R	ALS Functional Rating Scale-Revised
CDE	Common Data Elements
CFR	Code of Federal Regulations
CMSU	Clinical Materials Services Unit
CRF	case report form
CS	clinically significant
DM	data management
EAT-10	Eating Assessment Tool -10
EDC	electronic data capture
FDA	Food and Drug Administration
FOIS	Functional Oral Intake Scale
GCP	Good Clinical Practice
HIPAA	Health Insurance Portability and Accountability Act
ICF	Informed Consent Form
ICH	International Council on Harmonization
MedDRA	Medical Dictionary for Regulatory Activities
NINDS	National Institute of Neurological Disorders and Stroke
PAS	Penetration Aspiration Scale
ROSF	Riluzole Oral Soluble Film
SAE	serious adverse event
SOA	schedule of activities
VFSS	Videofluoroscopic Swallowing Study

CONFIDENTIAL INFORMATION

The information in this study protocol is confidential. Any disclosure, copying or distribution of the information contained within is strictly prohibited without written consent from MonoSol Rx LLC.

6. BACKGROUND AND PHARMACOKINETICS

Riluzole Oral Soluble Film (ROSF) is being developed by MonoSol Rx as an alternative dosage form with an alternate route of administration for the existing FDA-approved riluzole product, Rilutek[®] tablets. The ROSF product contains the active ingredient riluzole incorporated into a polymer-based film matrix utilizing MonoSol Rx's PharmFilm[®] technology. The inactive ingredient composition, the film dimensions, and the manufacturing process selected for this drug product are based on the information gained from the development of ROSF and other film products produced by MonoSol Rx (ZUPLLENZ[®] 4 mg and 8 mg and SUBOXONE[®] 2 mg/0.5 mg, 4 mg/1 mg, 8 mg/2 mg, and 12 mg/3 mg).

6.1. Rationale

The proposed indication for ROSF is the treatment of patients with Amyotrophic Lateral Sclerosis (ALS), the same as for Rilutek[®] (riluzole) tablets (US Package Insert; revision 04/2016). Clinical trials with Rilutek[®] tablets have shown that the time to tracheostomy or death was longer for ALS patients receiving Rilutek[®] compared to placebo, and there was an early increase in survival in patients receiving Rilutek[®] compared to placebo (Riviere 1998; Chen 2016; Watanabe 2015).

Amyotrophic Lateral Sclerosis (ALS) is a rare neurodegenerative disorder marked by the disruption of upper and lower motor neuron function. Riluzole is an FDA approved drug for treatment of the motor impairments of this disease and is taken by a sizable proportion of ALS patients. Given that dysphagia, or swallowing impairment, occurs in a reported 85% of ALS patients at some point during the disease progression, the ability to ingest riluzole medications can be compromised. Medications that can be easily administered orally without water may improve the quality of life of ALS patients and improve patient care. The riluzole oral soluble film may circumvent the potential inability of an ALS patient to swallow the tablet form of the medication, because the patient or caregiver need only to place the film on the tongue, where the active drug can immediately dissolve into the saliva and be ingested with intentional swallowing or during the normal reflex of swallowing, eliminating the need for swallowing a tablet with liquid or crushing it into soft food. (Appendix B) Absorption primarily occurs through the gastrointestinal tract after swallowing.

Therefore, the ROSF product has the potential to improve care and decrease daily burden on patients and caregivers.

6.2. Mechanism of Action

The mechanism by which riluzole exerts its therapeutic effects in patients with ALS is unknown (Rilutek[®] tablets, US package insert; revision 04/2016). Riluzole decreases the release of glutamate, thereby suppressing excitotoxicity. As oxidative stress and

CONFIDENTIAL INFORMATION

The information in this study protocol is confidential. Any disclosure, copying or distribution of the information contained within is strictly prohibited without written consent from MonoSol Rx LLC.

excitotoxicity are early events in ALS pathogenesis (Harikrishnareddy 2015), glutamate-mediated excitotoxicity has been postulated to be central to ALS pathogenesis, with motor neuron degeneration mediated by corticomotoneuronal hyperexcitability through transsynaptic anterograde processes (Eisen, 1992). According to Vucic and colleagues (Vucic 2013), because riluzole inhibits glutamatergic transmission, it may be expected that riluzole could exert modulating effects on the transcranial magnetic stimulation parameters of cortical excitability. Such a finding would then provide an objective measure of drug efficacy in ALS. However, the modulating effects of riluzole on cortical function in ALS have been varied. Specifically, while some studies have reported that riluzole partially normalizes cortical excitability (Desiato 1999; Stefan 2001), others have failed to establish any cortical modulating effects (Sommer 1999; Caramia 2000). In addition to direct anti-glutamatergic activity, riluzole appears to exert modulating effects on Na⁺ channel function (Cheah 2010). Given that increased Na⁺ channel conductance may contribute to neurodegeneration through Ca²⁺-mediated processes (Stys 2005, 2007), the Na⁺ channel blockade by riluzole may provide an additional neuroprotective mechanism in ALS. Of further relevance, riluzole may in part exert its anti-glutamatergic effects by inhibiting Na⁺ channel conductance and reducing glutamate release from presynaptic nerve terminals (Jimonet 1994; Cheah 2010).

6.3. Pharmacokinetics

According to the Rilutek® US package insert (revision 04/2016), riluzole is well absorbed with average absolute oral bioavailability of approximately 60% (CV=30%). C_{max} occurred at approximately 1.0 hour to 1.5 hours after administration (Le Liboux 1997, 1999). AUC values were linearly related to dose over a dose range of 25 mg to 100 mg. A high fat meal decreases absorption, reducing AUC by about 20% and peak blood levels by about 45%. The mean elimination half-life of riluzole is 12 hours (CV=35%) after repeated doses. With multiple-dose administration, riluzole accumulates in plasma by about twofold, and steady-state is reached in less than 5 days. Riluzole is 96% bound to plasma proteins over the clinical concentration range, mainly to albumin and lipoproteins

A human pilot bioavailability study (Study 1897) comparing ROSF 50mg with Rilutek® tablets 50mg found that the extent of absorption was approximately 14% greater and the rate of absorption was approximately 6% lower for the ROSF without water than for an intact Rilutek® tablet administered with 240 ml of water. When ROSF was administered with 240ml of water, the extent of absorption was approximately 9% greater and the rate of absorption was approximately 12% lower than for the intact Rilutek® tablet administered with 240 ml of water.

The pilot bioavailability study (Study 1897) was an open-label, randomized, single-dose, three-period, four-treatment, four-arm, incomplete crossover study. Sixteen adult, non-smoking subjects were enrolled, and all provided data valid for pharmacokinetic analysis. The four treatments were A: ROSF 50 mg administered without water; B: ROSF 50 mg administered with 240 mL water; C: Rilutek® 50 mg intact tablet administered with 240 mL

CONFIDENTIAL INFORMATION

The information in this study protocol is confidential. Any disclosure, copying or distribution of the information contained within is strictly prohibited without written consent from MonoSol Rx LLC.

of water; and D: Rilutek® 50 mg tablet, crushed, and administered with 15 mL applesauce. The objective was to compare under fasting conditions the bioavailability of the ROSF 50mg administered with or without water to that of the intact Rilutek® 50 mg tablet, administered with 240 mL of water, i.e., treatments A and B compared with treatment C.

For Treatment A (film without water) vs. Treatment C (intact tablet), Treatment A had approximate 14% higher extent of absorption of riluzole and an approximate 6% lower rate of the absorption of riluzole than Treatment C. The geometric mean T/R ratio for AUC_{0-t} and C_{max} was 113.70% with 90% CI 98.9-130.7%, and 94.36% with 90% CI 74.3-119.7%, respectively. For Treatment B (film with water) vs. Treatment C (intact tablet), Treatment B had approximate 9% higher extent of absorption of riluzole and an approximate 12% lower rate of the absorption of riluzole than Treatment C. The geometric mean T/R ratio for AUC_{0-t} and C_{max} was 108.6% with 90% CI 93.4-126.2%, and 88.1% with 90% CI 68.1-114.0 %, respectively.

Of note, in the pilot bioavailability study (Study 1897), inter-subject variability for ROSF 50mg without water for AUC_{0-t} and AUC_{0-inf} was reported as 25 and 26%, respectively, and for C_{max} , 38%. In contrast, inter-subject variability for the Rilutek® 50mg administered with 240 mL water for AUC_{0-t} and AUC_{0-inf} was reported as 39 and 40%, respectively, and for C_{max} , about 48%. The apparent difference between formulations in inter-subject variability remained when this comparison was limited to the eight subjects in Study 1897 who received both treatments. Intra-subject variability in pilot bioavailability study (Study 1897) was reported as 18 and 19% for AUC_{0-t} and AUC_{0-inf} , respectively, and 32% for C_{max} .

7. STUDY OBJECTIVES

7.1. Primary Objectives

Riluzole is FDA-approved for the treatment of patients with Amyotrophic Lateral Sclerosis (ALS). Riluzole extends survival and/or time to tracheostomy. ROSF (MonoSol Rx LLC) is a new formulation of riluzole that allows for rapid dissolution and release of active drug in the oral cavity. Since circumoral paresthesia and dry mouth have been reported with riluzole administered as Rilutek® tablets, the primary objective is to evaluate the effect, if any, of the new ROSF formulation on swallowing safety in subjects with ALS.

STUDY DESIGN

Approximately 30 subjects with ALS will be enrolled and undergo an instrumental evaluation of swallowing safety before and after administration of a single dose of the ROSF formulation containing 50mg of riluzole.

CONFIDENTIAL INFORMATION

The information in this study protocol is confidential. Any disclosure, copying or distribution of the information contained within is strictly prohibited without written consent from MonoSol Rx LLC.

